A daily list of expected clients will be generated from the master list for the study coordinators to locate those deemed eligible and who are due for a clinic visit. Once a client is located, a pre-baseline visit will be initiated with the study coordinator approaching the client and inquiring about their interest in participating in an ongoing study. On confirming interest, clients will be taken to a separate study room to verify their eligibility, and to receive their consent to participate. Consented participants will be given a medication event management system (MEMS) cap and instructed to store one of their HIV medications in a pill bottle with the MEMS cap attached. Additionally, they will be given a study appointment after approximately one month of this initial visit for adherence data retrieval and baseline survey administration. The first month of adherence data will be used as a baseline and the intervention will not begin before this follow-up visit.

Inclusion Criteria

The study sample will consist of male and female clients aged 18 and older who have started ART at Mildmay within the preceding three months. Treatment initiation is an important eligibility criterion given the conceptual framework of the pilot, which suggests that habit formation during initiation is a key driver for sustained ART adherence over time. Based on electronic records

data from Mildmay, each month at least 100-150 clients with these characteristics begin treatment at the hospital (for a total of 1,758 in 2018); therefore, a large pool of potentially eligible clients will be available for recruitment. Given the nature of the intervention, inclusion will also require participants to own, or have access to a phone at least five days a week throughout the duration of the intervention, while being willing to receive text messages throughout the intervention period.

Exclusion Criteria

Children under the age of 18 were excluded for two reasons: 1) the pediatric clinic is separate from the main recruitment site (which primarily caters to adult clients), and 2) the intervention might require alteration to account for the specific needs of children and adolescents.

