Additionally, clients who are not mentally fit to understand the consenting or study procedures, as well as clients who speak neither English nor Luganda (the local language spoken by the majority of people in and around Kampala) were excluded. As both intervention groups rely on the receipt of text messages, clients who don't own a cell phone or have access to one will also be excluded.

Participation in another adherence study as well as non-ability or non-desire to use MEMS caps regularly throughout the course of the study will also be a basis for exclusion. Consequently, if the baseline MEMS reading suggests that participants opened their pill bottle less than 30% of days, and if that was not a consequence of low adherence, then the participant will be given a transport refund and will be unenrolled from the study. Finally, clients coming outside regular clinic working hours will be excluded.

Randomization and Allocation

Participants will be randomly assigned to either one of the treatment arms (T1 = *Messages*; T2 = *Incentives*) or the control arm after consenting but will only be informed of their assignment after the baseline survey is over to minimize any potential influence of the assignment on the baseline survey responses. The distribution ratios for the randomization will be 1:1:1 and the assignment will be carried out through a computer-generated randomization component built into the baseline survey administration software, called Questionnaire Development System. The random assignment (to either the control group or one of the two intervention arms) will be revealed at the end of the baseline survey to both the participant and the study coordinator, who will therefore not know the respondent's treatment assignment during the survey. Given the

nature of the intervention, neither the interviewers nor the participants can be blinded to the treatment status. However, the data analyst who will conduct the impact analysis will be blinded to treatment assignment.

Procedures

Interventions

The pilot will include a control arm, along with two intervention arms – *Messages* (T1) and *Incentives* (T2).

Control Group: Usual Care

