Participants assigned to this arm will receive care as usual, including the adherence support mechanisms that are part of usual care practices. At recruitment, participant will be educated about the importance of pill-taking using a leaflet that details information on how to establish healthy pill-taking routines. Participants will then be asked to select one of the following three pill-taking anchors: getting dressed in the morning, eating a meal (breakfast) in the morning, or eating dinner in the evening, which will also be described in a habit leaflet, and they will be asked to specify the time at which their anchor typically occurs. Once selected, participants will be asked to continue using their MEMS caps and to bring the caps during the next visit.

During each of the subsequent study visits, scheduled roughly one month apart during the intervention period and 1-3 months apart subsequently, participants will be asked a short questionnaire inquiring about changes in their ART adherence behavior, including any changes in location, times, and social activities surrounding their pill-taking behavior and their ART adherence habit strength. They will also be asked about any clinical changes to their ART regimen, as well as about their daily MEMS cap usage. This is because pill-pocketing (dispensing of more than one dose in a given bottle opening event) is a common phenomenon among the population, with 15% of a previous study sample reporting pocketing [48]. If participants indicate pocketing, the study coordinator will work with the participant to find another solution to avoid pocketing and continue using their MEMS cap, and we will adjust for their pocketing in our assessment of their adherence outcomes. Finally, participants will be asked about any changes to their contact information or addresses, and updates will be noted in the contacts data.

The study coordinator will then download the readings from the MEMS cap, inquire about the participants' next visit, and remind them to continue taking their pills on time. This procedure will be carried out throughout the intervention and post-intervention periods.

Treatment Group 1: Messages Group

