Participants assigned to this arm will receive daily text messages in addition to care as usual during the three-month intervention period. When the participant is informed of their treatment assignment, they will be educated on the same habit leaflet as all other study groups and asked to pick an anchor and share the time of the day the anchor typically occurs. In addition, the study coordinator will register the participant's cell phone number along with their language preference for text messages (English or Luganda) on an online text messaging system, Twilio. The system will include programmed text messages that will be sent to all participants at 2pm local time every day for the three-month intervention period. Table 1 shows some example text messages, each of which would be sent on a specific day of the week. Once registered, the study coordinator will send the participant a test message to confirm registration. If for any reason the participant is unable to confirm receipt of the test message (for example, if their primary number is owned by another person that they live with), the study coordinator will try registration again. If the registration is still not confirmed, the participant will be unenrolled from the study.

Table 1: Example Text Messages for the Messages and Incentives Groups

Hello, this is INMIND. Take your vitamins together with your existing routine for good health!
Hello, this is INMIND. Forming routines requires effort now but will pay off in the end!
Hello, this is INMIND. Don't forget to take your vitamins every day at the same time!
Hello, this is INMIND. Remember to stick with your healthy plans!

During each subsequent intervention-period study visit for the enrolled participants, participants will be asked about the text messages in addition to the questions asked to the participants in the control group. Specifically, participants will be asked whether they have been receiving the text messages and whether they read them. MEMS data will also be downloaded during each of these subsequent clinic visits.

Treatment Group 2: Incentives Group

Participants assigned to this arm will receive monetary incentives in addition to daily text messages (as with the *Messages* arm) and care as usual, during the three-month intervention

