period. Upon revealing their group assignment, participants will be registered on the Twilio platform following the same procedures as outlined for the *Messages* arm. Participants will also be informed that if at their next visit they have taken their medication on 70% or more of the last 30 days within +/- one hour of their chosen anchor time, then they will be eligible to participate in a lottery to win mobile airtime. The study coordinator will note that they will receive three opportunities to participate in the lottery (i.e. at each study visit over the next three months, if they are eligible). To ensure participants understand the process, the study coordinator will carry out a mock prize drawing wherein participants will choose from one of three cards listing an airtime prize amount. The chosen card and corresponding prize will be revealed to the participant, and the amount listed on the card will be sent to the participant's phone number (via Reloadly) in the form of a mobile top-up balance.

During each subsequent study visit, the study coordinator will check the client's MEMS cap data and fill out a form that asks questions about adherence behaviors (as with the control group), and text messages (as with the *Messages* group). The study coordinator will also ask about pill pocketing to assess prize eligibility. To avoid unfairly punishing participants who pocket doses (resulting in an under-reporting of MEMS data in the software), participants will be asked about an estimated number of doses pocketed and will be allowed to enter one wild card prize drawing when they did not reach the adherence threshold. They will be specifically informed that this will be a one-time exception. After the three-month intervention, participants will follow the same procedures as the Control and *Messages* groups.

MEMS-cap procedures

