The MEMS data will be automatically downloaded and stored electronically using the MEMS cap software that will be installed on a tablet accessible by the study coordinator. The other study data, including participants’ survey responses, monthly visit reports, and other information about study dropout, will be recorded by study personnel in Microsoft Access templates designed by the research team. These electronic data will be safely stored at Mildmay and securely transferred to the research team in the United States periodically during the study period, and at the end of the nine-month study.

Chart Abstraction

Participant’s viral load will be used as a complementary measure to the MEMS data for the assessment of ART adherence. They are now a part of routine clinical care at Mildmay with tests carried out when someone receives a positive HIV test result, after six and 12 months of the initial diagnosis, and every 12 months thereafter. Consequently, the results of the viral load

test will be chart abstracted and the data abstraction will be timed with the routine tests for the participants.

[Participant Tracking](#)

Extensive tracking information will be collected at recruitment and will be verified at each study visit. This will include mobile phone numbers, home address, and email addresses, as well as the contact information for two individuals who live in the same community and who the participant is comfortable and familiar with. These additional contacts are collected to ensure that the participant can be located in case their contact information changes. These procedures have limited attrition in the researchers' previous studies to about 5% [44,48].

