If a participant in either treatment group loses, breaks, or otherwise cannot use their mobile phone, then they will no longer be able to receive text messages as part of the intervention. To respond to this possibility, the study coordinator will record the functionality of participants' mobile phones at each monthly visit and those with missing or broken mobile phones will be noted. Also, all active phone numbers of the participants (as it is not unusual for Ugandans to use more than one SIM card and/or phone) will be recorded to ensure an alternative means of delivering the messages exists, when available. Additionally, participants will be given a handout at the start of the study explaining that they should give the study team a call if they switch phones or phone numbers at any point during the first three months of the study, and that they will be rewarded with 3,000 USh for notifying the study coordinators of such a change.

Outcomes

The study will assess the following outcomes:

Feasibility and Acceptability

The feasibility and acceptability of the INMIND intervention will be assessed by the study retention rate and the attendance rate for scheduled clinic visits, as well as through survey responses collected at the end of the three-month intervention, and following the six-month post-intervention period. These survey measures ask participants about their ability to understand all intervention materials and their perceived value of the intervention. We will also conduct focus groups with a sample of study participants after the post-intervention survey to collect additional information on the study's feasibility and acceptability.

Preliminary Efficacy

Primary Outcome 1: Electronically measured mean medication adherence during intervention

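### Only the two text arms can lose participants to a failed test message after allocation is revealed, so comparisons with control may not be as randomised; the bias is probably small, but the analysis population is undefined

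*Combined protocol and SAP*

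**What the plan says.** Under Randomization and Allocation, the assignment "will be revealed at the end of the baseline survey to both the participant and the study coordinator". What follows differs by arm.

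- **Messages** (Treatment Group 1). Once told the assignment, the participant is registered on the texting platform and sent a test message. If receipt cannot be confirmed, registration is tried once more. "If the registration is still not confirmed, the participant will be unenrolled from the study". The example given of a failure is a primary number that belongs to someone else in the household.
- **Incentives** (Treatment Group 2). "Upon revealing their group assignment, participants will be registered on the Twilio platform following the same procedures" as in the Messages arm.
- **Control** (Usual Care). After choosing an anchor there is no phone step: "Once selected, participants will be asked to continue using their MEMS caps and to bring the caps during the next visit".

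Several provisions apply to all arms. Under Inclusion Criteria, every client must "own, or have access to a phone at least five days a week throughout the duration of the intervention". A second condition there concerns the texts themselves: "while being willing to receive text messages throughout the intervention period". Participant Tracking collects contact details at recruitment and checks them at each visit: "This will include mobile phone numbers, home address, and email addresses". For message delivery, all active numbers "will be recorded to ensure an alternative means of delivering the messages exists, when available".

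On analysis, Statistical Methods and Analyses plans covariance models adjusted for characteristics found to differ between groups at baseline. Handling Missing Data and Attrition restricts imputation to participants still enrolled, and provides nonresponse weights for dropout if dropout proves non-random. Neither section states which randomised participants are analysed, or whether removal by study staff is dropout.

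**The concern.** Randomisation makes the arms comparable as assigned. A rule that can remove people after assignment is known, and in two of the three arms only, can undo that. Controls who would have failed the same check stay in and cannot be identified, so a filtered text arm is set against an unfiltered control arm.

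This touches each text arm against control, and the pooled text arms against control, for the four primary adherence and routinisation outcomes and the two secondary outcomes. Messages against Incentives is less exposed, because both arms follow the same rule.

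It also affects feasibility. The study retention rate is a feasibility measure, and the plan does not say whether people removed because a text could not be confirmed count in its denominator. Failure to receive the texts is itself feasibility information.

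**Working it through.** **1. Order of events.** Participants are assigned, the assignment is revealed at the end of the baseline survey, and only then are the text arms registered and tested. The removal rule therefore acts after randomisation and after disclosure. The other removal rule, for low baseline cap use, is not arm-specific. Phones that fail later are recorded, and no removal is described, so this filter acts once.

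**2. Do the common safeguards remove the asymmetry?** They should keep the count low. But the phone criterion accepts access without ownership, so it admits the shared-phone users whom the Messages section gives as its example of failure. No text is tested before randomisation, and the plan does not say that the second attempt uses a different number.

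**3. The plan's own benchmark.** Sample and Effect-size Estimation gives a detectable difference of 9 points for pooled text arms against control, with SD 20, 150 participants, 10% attrition and 80% power, two-tailed. Alpha is not stated; I take 0.05. With 90 against 45:

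(1.96 + 0.84) × 20 × √(1/45 + 1/90) = 10.2 points.

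Without attrition (100 against 50) the result is 9.7. The 9-point figure does not reproduce from its stated inputs, so I do not rest anything on it.

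**4. Size of the bias.** Let f be the share of a text arm removed and D the mean adherence of those kept minus that of those removed. The kept mean exceeds the as-randomised mean by f × D. The documents give neither quantity, so the values below are assumptions. Outcome SD 20 and 10% attrition are the plan's.

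SE = 20 × √(1/45 + 1/[90(1 − f)]); type I error = P(|Z + bias/SE| > 1.96), unadjusted, pooled text arms against control.

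| f | D | Bias (points) | SE | Type I error | Without attrition (50 v 100(1 − f)) |
|---|---|---|---|---|---|
| 2% | 10 | 0.2 | 3.66 | 0.0503 | 0.0504 |
| 5% | 10 | 0.5 | 3.68 | 0.0521 | 0.0523 |
| 10% | 20 | 2.0 | 3.72 | 0.0837 | 0.0876 |

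The last row is a pessimistic case with no support in the documents. For one text arm against control, with attrition, the three type I errors are 0.0503, 0.0516 and 0.0748. A negative D reverses the sign of the bias.

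**5. Extreme bounds.** Adherence runs from 0 to 100. With an illustrative observed text-arm mean of 75, the as-randomised mean lies between (1 − f) × 75 and (1 − f) × 75 + 100f:

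- f = 2%: 73.5 to 75.5, so the bias is between −0.5 and +1.5 points.
- f = 5%: 71.25 to 76.25, so the bias is between −1.25 and +3.75 points.

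**6. Would baseline adjustment catch it?** The plan does not say how differing characteristics are identified. If it were a 5% test, and the same gap were present in baseline adherence (SD 20 assumed, before attrition), the shift would be flagged in 5.0-5.2% of trials at f = 2-5%, D = 10. That is hardly above chance, so the adjustment is not a dependable safeguard.

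**The case against.** The case for leaving this alone has four parts.

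*The numbers are practically nominal.* At 2-5 removals per 100 text-arm participants and a 10-point gap, type I error barely moves. This is a pilot whose sample-size section admits limited power. That stands: on bias alone the point is minor. What raises it is the undefined population together with a stated rule that treats the arms differently.

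*No removal is reported.* Also correct. A reader might infer that the control comparisons are already compromised. The documents support only a conditional statement: if anyone was removed, they may not be as randomised.

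*Dropout is already handled.* Study staff record information on dropout, and the attrition section is not confined to voluntary withdrawal, so reading it to include these removals is natural. But it does not say so, the weights depend on dropout first being found non-random, and imputation excludes people no longer enrolled. One clarifying sentence would settle the first of these.

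*The remedy cannot recover the main outcomes.* Data collection is complete, and cap data after unenrolment probably do not exist. This stands and limits what the fix can claim. For the same reason, any dilution from keeping people who never received texts could not be observed in this trial's primary outcomes.

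**Conclusion.** The plan should be corrected on this point. The asymmetry is in the text: removal for an unconfirmed test message follows disclosure, applies to both text arms, and has no control counterpart. No section defines an as-randomised population or says that removal by the study is dropout.

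Under the assumed 2-5% removed and 10-point gap, the bias is 0.2-0.5 points and type I error is 0.050-0.052, so the effect is probably small. That judgement would not hold at 10% removed with a 20-point gap (2.0 points, 0.084 with attrition), but nothing in the documents points to such a case. A by-arm count would show which situation applies.

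Two stronger readings should be resisted. One is that the rule flatters the intervention. It does so only if those removed adhere less than those kept; if they adhere more, it works against the intervention, and the documents do not say which. The other is that analysing everyone as randomised would restore the primary comparison. With the adherence outcomes of those removed probably missing, it can only be bounded.

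**What to change.** For this trial, while analyses are ongoing:

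1. Define the analysis population as all participants randomised, in their assigned arm.
2. State that unenrolment by the study counts as dropout under Handling Missing Data and Attrition, and stays in the denominator of the study retention rate.
3. Report these unenrolments by arm, with baseline cap-measured adherence. Someone other than the blinded analyst should prepare the table.
4. Add a sensitivity analysis for their missing adherence outcomes over plausible values, with 0 and 100 as the extremes, and say that it bounds the primary comparison without repairing it.
5. Where consent allows, keep them for retention in care and viral suppression, which come from clinic records. The consent text is not available here, so this item is conditional.

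For the planned larger trial: confirm a test text in all consenting clients before randomisation, as a common eligibility check.

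The cost now is a few lines of wording, one table, one sensitivity analysis and possibly a few extra chart abstractions, which would reopen collection already marked complete. In the larger trial it is one additional text per control and a few clients screened out before randomisation.

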newly diagnosed clients who are getting accustomed to ART treatment. During the post-intervention period, the team will follow participants and continue MEMS data collection during the participants' regular clinic visits (expected to be every month for the first six months post treatment initiation, and every one-to-three months thereafter) for a period of six months, bringing the total study period to nine months.

Since the long-term goal of the study is viral suppression, viral load data will also be collected during the routine assessment. Viral load tests for treatment initiators are conducted after the first six months of ART initiation, and then switched to 12-month periods as per clinic and Ugandan Ministry of Health guidelines. Survey assessments will be administered at baseline, month three, and month nine for all participants.

It is important to note that the pilot study is being preceded by a formative phase, and succeeded by an adaptation phase, both of which are geared towards collecting qualitative data pertaining to the overall design, feasibility, and acceptability of the interventions. The results of the formative phase will be used to adapt the pilot intervention materials and timeline prior to the intervention administration. The adaptation phase is expected to provide feedback on the mission critical parameters of the interventions, which would be utilized to mold the intervention in preparation for a full-scale randomized controlled trial. Figure 2 gives the timing of study activities.

Study Sites

The study will be performed at the Mildmay, Uganda, an HIV clinic in Kampala, Uganda. This clinic specializes in providing comprehensive HIV and AIDS prevention, care, and treatment services to over 105,000 HIV-infected patients. It offers integrated health services to a diverse population base; of the 15,000 patients served at the main site in Lweeza, 11% are children younger than 18 years, 65% are female, and 100% of patients are on ART. Mildmay also has well-established electronic medical records infrastructure, making it one of the growing number of facilities using electronic medical record systems in Uganda.

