The fourth outcome will be calculated using the same procedures as *Outcome 3*. However, the data from which the measure will be assessed will be collected during the post-intervention period.

The team will also assess two secondary efficacy measures, as described below:

Secondary Outcome 1: Retention in care

Retention in care is an important metric of treatment adherence. Failure to remain in care is a commonly observed problem for treatment initiators. To assess how well participants will continue to remain in care, Mildmay electronic records will be used to evaluate the number of study participants who fail to observe their regularly scheduled clinic visits. Participants who don't make any clinic visits for six months or more will be considered lost to follow up. The study coordinator will call them using the tracking information collected for the study to inquire about their reason for stopping care at the Mildmay clinic. This outcome will be measured as an indicator of whether the participants are still active clients at the clinic at the end of the nine-month study.

Secondary Outcome 2: Viral Suppression

HIV RNA (viral load) is our final outcome measure. According to the AIDS Clinical Trials Group, virological failure is defined as a confirmed viral load > 200 copies/mL. Below this level, the viral load is considered undetectable. Importantly, this is a reliable biological measure of ART adherence, since strong adherence leads to lower viral load. Given the intervention design, viral load will be an important complementary measure of adherence. The analysis will examine the intervention effects on the likelihood of being virally suppressed at the end of the nine-month study period.

Data Analysis

[Statistical Methods and Analyses](#)

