Feasibility and acceptability will be analyzed using summary statistics derived directly from our self-reported measures. To estimate preliminary efficacy, statistical analyses comparing group-level differences in the secondary and tertiary outcome measures will be performed. An Analysis of Covariance framework will be used to test for group differences in each secondary and tertiary outcome, controlling for the participant characteristics that are found to differentiate the groups at baseline. For analyses of dichotomous variables, such as viral suppression, a non-parametric McNemar's test and an analogous multiple logistic regression will be used to control for covariates to assess group differences. In addition to static comparisons of group means for each outcome at three-month intervals, the longitudinal nature of the data will be leveraged by using repeated measures and time-series techniques. Specifically, a linear mixed model with repeated observations will be fit using maximum likelihood through 'xtmixed' in the

software package Stata to study group-level temporal dynamics in daily measures of the primary and secondary outcomes.

Sample and Effect-size Estimation

We will recruit a total of 150 participants and will assume a 90% retention rate through the 9-month study period. This is a conservative estimate of attrition, as previous research in the same clinic and with a similar population observed only 6% attrition over 12-month study periods [44,48]. Given the study objectives of establishing acceptability, feasibility, and preliminary effectiveness, the targeted sample size may not have the power to detect many of the effects that would be clinically significant. Nonetheless, effect size calculations associated with 80% power (2-tailed test) with regard to the primary outcomes at month nine have been carried out. A recent study conducted at Mildmay suggested that mean ART adherence rates are ~ 75% (SD = 20) as measured by MEMS caps [44]. Using these parameters as estimates of adherence for the control group, and 10% attrition at month nine, a sample size of 150 will provide sufficient power to detect a 9% difference in mean adherence between the pooled intervention groups and the control group (effect size = .47), and a roughly 11% difference in mean adherence between the two intervention groups. This translates to the study being able to detect medium effect sizes.

Qualitative Analysis

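### Retention in care is scored as being an active client of one clinic, so a participant who has transferred and is still in care elsewhere can count as not retained

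*Combined protocol and SAP*

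**What the plan says.** The section on Secondary Outcome 1 (Retention in care) states its purpose, its data source and its scoring rule.

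- Purpose: "To assess how well participants will continue to remain in care".
- Source: "Mildmay electronic records will be used to evaluate the number of study participants who fail to observe their regularly scheduled clinic visits".
- Loss to follow-up: participants who do not "make any clinic visits for six months or more will be considered lost to follow up". The study coordinator telephones these people "to inquire about their reason for stopping care at the Mildmay clinic".
- Score: an indicator of "whether the participants are still active clients at the clinic at the end of the nine-month study".

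Under Study Design, post-intervention follow-up runs "for a period of six months, bringing the total study period to nine months". Under Statistical Methods and Analyses, dichotomous outcomes are compared between groups with McNemar's test and a multiple logistic regression. Handling Missing Data and Attrition deals with study dropout in general terms. No section gives a rule for transfer to another facility, whether as a separate category, an exclusion, a censoring rule or a sensitivity analysis.

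**The concern.** The stated purpose concerns care; the score concerns one clinic. On the plain reading of the indicator, a person taking ART at another facility is not an active client and receives the same score as a person who stopped treatment. The one item of information that could separate them, the reason given at the tracing call, is collected but has no stated use in the outcome.

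This is one of two secondary efficacy measures, it is to be compared between arms, and the findings are to inform a larger trial. Failures are likely to be few, so a handful of transfers could be a large share of them. If transfers have little to do with text messages or prize drawings, they add failures that the interventions cannot change.

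**Working it through.** The plan states no rate, effect size or power for this outcome, so there is no figure to reproduce. The check has two parts.

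**1. When would a transferred participant be scored as a failure?** *Active client* is not defined beyond the six-month loss rule, which leaves two readings.

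- *Active* means still attending visits as scheduled. A participant who transfers before the last scheduled visit is then scored as not retained.
- *Active* means not lost to follow-up. To be lost by month nine, the last visit must fall at or before month 9 − 6 = 3. A participant who transfers after about month three is then still scored as active. This agrees with their true status only by accident, because someone who stopped treatment after month three gets the same score.

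The same date limits the tracing call. A participant last seen after about month three has not reached six months without a visit by month nine, so the rule does not yet trigger a call.

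**2. What would misclassified transfers do to the comparison?**

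Inputs from the documents: 150 participants allocated 1:1:1, so 150 / 3 = 50 per arm. Inputs assumed, because the documents give none: true disengagement of 5% in an intervention arm and 10% in control, and transfers scored as failures adding the same t percentage points to both arms.

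Formulas, with a = 0.05 + t and b = 0.10 + t:

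- Difference = b − a
- Odds ratio = [a / (1 − a)] / [b / (1 − b)]
- Standard error of the difference = √{[a(1 − a) + b(1 − b)] / 50}

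| t | a | b | Difference | Odds ratio | Standard error |
|---|---|---|---|---|---|
| 0 | 0.05 | 0.10 | 0.05 | 0.0526 / 0.1111 = 0.47 | √(0.1375 / 50) = 0.052 |
| 0.03 | 0.08 | 0.13 | 0.05 | 0.0870 / 0.1494 = 0.58 | √(0.1867 / 50) = 0.061 |
| 0.05 | 0.10 | 0.15 | 0.05 | 0.1111 / 0.1765 = 0.63 | √(0.2175 / 50) = 0.066 |
| 0.08 | 0.13 | 0.18 | 0.05 | 0.1494 / 0.2195 = 0.68 | √(0.2607 / 50) = 0.072 |

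The absolute difference does not move. The odds ratio, which is what the planned logistic regression estimates, moves toward 1, and the standard error of the difference grows. In people, t = 0.05 is 50 × 0.05 = 2.5 per arm, against 2.5 and 5 true events.

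**The case against.** The strongest reply is that clinic-recorded status is stated openly and ascertained the same way in every arm. Replacing it with a reason given by telephone introduces self-report, collected by staff who know the allocation and only from people who can be reached. Reporting or reachability could then differ by arm. This stands as a real cost, and it is why the clinic-only indicator should be kept.

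The assumed rates may also be high. The protocol cites about 5% attrition in earlier studies and 6% over 12 months at the same clinic, whereas the illustration has 13% to 18% scored failures in control. Study attrition is not clinic retention, but it is the nearest figure available. In addition, power for 5% versus 10% with 50 per arm is only about 16% before any transfers, and the protocol itself concedes limited power. So no confirmatory conclusion turns on this; what is affected is the estimate and its interpretation.

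A reader might also infer four stronger points that the documents do not support:

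- That every transfer is misclassified however *active* is dated. Under the six-month rule, a transfer after about month three could still score as active.
- That the feasibility assessment is understated too. It uses the study retention rate and attendance at scheduled visits, not this indicator. Likewise, the sample-size statement "We will recruit a total of 150 participants and will assume a 90% retention rate through the 9-month study period" concerns study retention.
- That everyone who leaves is asked why. The call is specified only for people with no visit for six months or more.
- That a real difference is diluted on every scale. With equal added percentage points, the absolute difference is unchanged.

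**Conclusion.** The point holds in a limited form. The outcome is justified as retention in care and scored as retention at one clinic, with no transfer rule and no use of the leaving reason. Some participants still in care elsewhere can therefore be counted as failures, and which ones depends on the timing of the transfer and on an undefined term.

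Under the assumed rates, the odds ratio would be pulled from 0.47 to between 0.58 and 0.68. That rests on three assumptions the documents cannot confirm: the disengagement rates, the transfer rates, and transfers being similar across arms. If transfers differed between arms, even by chance, the absolute difference would shift as well. Confidence in the size is low; confidence in the gap between the stated purpose and the score is high. It is a minor, worthwhile repair to the definition of one secondary outcome.

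**What to change.** Amend the definition of Secondary Outcome 1 as follows.

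1. Tie *active* at month nine to a stated visit rule.
2. Classify documented transfers as retained in care, where the evidence is a clinic transfer record or the reason given at the planned tracing call.
3. Count deaths as not retained, but report them separately.
4. Count everyone else who is not active as not retained.
5. Keep the clinic-only indicator as a sensitivity analysis, and report transfers by arm and by source of evidence.

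The cost is a few lines of analysis-plan wording and a reason code taken from records and calls already planned. The protocol reports data collection complete in August 2023 with analyses ongoing, so the rule should draw on what has been recorded and should not depend on new calls. Leavers never reached, with no transfer record, fall under item 4. The rule should be fixed before this outcome is compared between arms; if that comparison has been made, the revised version should be labelled post hoc.

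The downside is that self-reported transfer may be overstated or may differ by arm. Comparing the result with the clinic-only analysis shows how much that matters.
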